## **5. Subject Enrollment**

The study procedures will be carried out remotely using a Zoom Enterprise Partners account or in person. Prior to the first visit, we will perform a phone screening to determine eligibility of prospective study volunteers. Individuals will be informed that identifiable information may be recorded during the phone screening. If a subject is deemed eligible, identifiable information (e.g. name, contact info) will be collected, and an informed consent form will be emailed to subjects for review. Baseline testing at a future date will be scheduled.

Eligible subjects will undergo the informed consent process in person, by phone or on Zoom Enterprise with a trained research assistant at the beginning of the baseline testing visit. Once consented, subjects will undergo baseline assessments (visit #1) in person using REDcap Survey. After baseline testing, subjects will participate in the Tele-TC intervention, with recommended training sessions at least three times a week, along with two or more supplementary one-on-one live sessions (lasting upwards to 45 minutes) with TC instructors. TC proficiency using wearable sensors will be assessed at visit #1 baseline, at two follow-up assessments (visit #2 and visit #3) at approximately 4 and 8 weeks, and at a final assessment (visit #4) at 12 weeks. A semi-structured qualitative interview will also be performed at visit #1 and #4.

[figure not shown]

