## 2. Assessments (Visits #1B, #2, #3 and #4)

At *Visit #1B*, subjects will be instructed in how to use the tablet-based Tele-TC program. The mobile devices and the sensors will be provided to each participant and will be preprogrammed with all required software. It is worth emphasizing that, as part of the consent process, all subjects will be asked permission to be videorecorded during the assessments via Zoom Enterprise.

Visits will be divided into two components: 1) clinical assessments and 2) instrumented monitoring of TC performance.

The following clinical assessments will be performed during *Visits #1B and #4*.

The following questionnaires will be provided to the subjects through REDcap Survey with an email link. It will take around 45 minutes to complete all of the questionnaires.

- *Activities Specific Balance Confidence (ABC)*: 16-item self-report measure in which patients rate their balance confidence for performing activities.
- *PROMIS® (Patient-Reported Outcomes Measurement Information System) 29 (PROMIS-29)* instrument: 29-item questionnaire assessing each of the following domains: anxiety, depression, fatigue, physical function, pain interference, pain intensity, sleep disturbance, and ability to participate in social roles and activities. The instrument contains four items from each primary domain plus a single pain intensity rating.
- *Physical Activity Scale for the Elderly (PASE)*: self-reported level of physical activity in individuals aged 65 years or older during the previous 7 days.
- *Exercise Self-efficacy Questionnaire (SEE)*: A 9-item questionnaire that focuses on the self-efficacy expectations for exercise for older adults; specifically, the ability to continue to exercise despite barriers.

*Clinical assessments which take around 15 minutes will include tests such as:*

- *Trail Making Test A/B*: Executive function will be assessed using the Trail Making Test. Participants will be timed while sequentially connecting a series of numbered circles (part A), as well as connecting an alternating series of numbers and letters (part B). The adjusted trail making score (i.e., part B minus A, sec) is sensitive to changes in executive function and frontal lobe pathology in older adults. The trail making Test will be camera-recorded.

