- *Controlled Oral Word Association Test (COWAT)*: examines working memory span. COWAT requires the participant to produce as many words as possible that begin with a given letter of the alphabet (F,A,S). There is 1 minute allowed for each of the three letters. The score is the sum of all acceptable words produced in the three trials. COWAT has good reliability and validity. The test will be audio-recorded and transcribed to ensure accurate collection of subjects' verbal responses.
- *Digit Span Test*: widely used measure of short-term memory, i.e. the number of digits a person can absorb and recall in correct serial order. Two trials of eight number sequences

are read aloud. The number sequences start out easy, with just two numbers, and get progressively more difficult, the last being nine digits. Scores are based on the number of sequences correctly recalled (i.e., until the participant consecutively fails two trials of the same digit span length). BDS has good reliability and validity.

- *Grip Strength:* we will measure the grip strength of both upper limbs using a hand grip dynamometer. We will repeat the measure three times.
- *Instrumented and camera-recorded monitoring of balance in each leg separately:* Subjects will be asked to stand on one leg for 30 seconds.
- *Instrumented and camera-recorded Timed-Up-and-Go:* Subjects will be asked to stand up from a chair, walk at their normal speed around a cone, turn around, and come back to sit in the chair.
- *Instrumented and camera-recorded Timed-Up-and-Go dual task:* Subjects will be asked to complete the previous task while counting backwards by three.
- *Instrumented and camera-recorded Sit-to-Stand:* Subjects will be asked to stand up from a chair while keeping their arms crossed across their chest during 30 seconds.
- *Instrumented and camera-recorded monitoring of balance in both legs* with feet shoulder-width apart and as close as possible without touching.
- *Instrumented and camera-recorded monitoring of gait:* Subjects will be asked to walk back and forth for 2 minutes.
- *Instrumented and camera-recorded monitoring the miniBEST:* It is a shortened version of the Balance Evaluation System Test (BESTTest). It is a 14-item test scored on a 3-level ordinal scale. It aims to target and identify different balance control systems.

Instrumented and camera-recorded monitoring of TC performance will be performed during Visits #1B, #2, #3 and #4:

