## ***7. Data variables analysis to be collected***

The primary outcomes of the study are the retention and the protocol adherence during the study, and the System Usability Scale collected post-intervention.

The exploratory outcomes will include the following:

- The ease of use of the Tele-Tai Chi platform measure with the qualitative interview collected post intervention.
- The changes in outcomes collected at baseline and post-intervention: the Activities-specific Balance Confidence (ABC) scores, PROMIS 29 scores, the Physical Activity Scale for the Elderly (PASE), the Trail Making Test A/B scores, Self-Efficacy Exercise (SEE) scores, the grip strength, the Controlled Oral Word Association Test (COWAT), the Digit Span Test, the Timed-Up-and-Go, the Timed-Up-and-Go dual task single leg stance, the Sit-to-Stand performance, the balance on both legs with feet shoulder-width apart, the balance on both legs with feet close to each other, the normalized-to-height stride length and stride time variability, the activity level, and the Mini-Balance Evaluation Systems Test (MiniBEST) collected only in individuals who are willing to be tested in the MAL.
- The changes in The Tai Chi proficiency scores collected at baseline, 4 weeks, 8 weeks, and post-intervention.

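### The COWAT uses one letter set (F, A, S) at baseline and week 12 in a single arm, so its exploratory change score can contain retest gain that counterbalanced letter sets would cheaply reduce

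*Combined protocol and SAP*

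**What the plan says.** Section 6, subsection 2 (Assessments) opens the clinical battery with "The following clinical assessments will be performed during" Visits #1B and #4. Section 5 places the second occasion: "and at a final assessment (visit #4) at 12 weeks".

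The three cognitive tests are described in different detail:

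- **COWAT.** The letters are named: "COWAT requires the participant to produce as many words as possible that begin with a given letter of the alphabet (F,A,S". Scoring is a word count: "The score is the sum of all acceptable words produced in the three trials". No second letter set is given.
- **Trail Making.** The score is a time: "The adjusted trail making score (i.e., part B minus A, sec) is sensitive to changes in executive function and frontal lobe pathology in older adults". Nothing is said about which layout is used at which visit.
- **Digit Span.** The structure is given ("Two trials of eight number sequences"), but not whether the same digits return at Visit #4.

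Section 6, subsection 7 lists all three among the exploratory outcomes under "The changes in outcomes collected at baseline and post-intervention". Hypothesis 2 of Aim 4 (Section 2) expects clinically relevant change at 12 weeks. Section 9 plans descriptive statistics and correlations with the sensor metrics. Section 3 describes a single-arm study of 20 people. The assessment, outcome and analysis sections mention no alternate form, practice run, second baseline or adjustment for practice.

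**The concern.** Word generation from a given letter can improve on a second attempt because the participant remembers words or strategies for that letter. As written, every participant meets F, A and S at both visits. A higher COWAT score is better, so any such gain looks like benefit. Without a control group the gain and the programme effect sit in the same mean. Descriptive reporting does not help, because the bias is in the mean itself.

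What is at stake is the reading of one exploratory result, the COWAT part of Aim 4 Hypothesis 2. This is worth separating from the general limits of a single-arm study: a control group would be a different and larger trial, whereas the choice of letters is a test-administration detail that can be changed at almost no cost.

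**Working it through.** **What the plan states.** It gives no power calculation, alpha, SD, retest correlation or practice-effect size, and 20 is a convenience sample. There is no figure to reproduce.

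**Structure of the bias.** Let T be the programme effect on COWAT, s the gain from repeating the same letters, and g the gain from familiarity with the task, tester and setting.

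- Same letters at both visits: expected change = T + g + s.
- Two letter sets differing in difficulty by δ: expected change = T + g + δ in one order and T + g − δ in the other. The average of the two order means is T + g.

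Counterbalancing removes s, and keeps δ out of the mean. It leaves g, which a single arm cannot separate from T.

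**Illustrative size.** Inputs from the protocol: n = 20 (Section 3), and n = 20 × 0.8 = 16 if withdrawals reach the 20% limit in Aim 1 Hypothesis 1. Assumed inputs: a total practice gain of 0.1 to 0.4 baseline SD, retest correlation r of 0.6 to 0.8, equal SD at both visits, T = 0, and a two-sided 5% paired t-test.

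SD of change = √(2(1 − r)) = 0.894, 0.775 and 0.632 baseline SD for r = 0.6, 0.7 and 0.8.

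95% half-width for mean change = t × SD / √n:

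- n = 20: 2.093 × 0.894 / √20 = 0.42 at r = 0.6, and 2.093 × 0.632 / √20 = 0.30 at r = 0.8.
- n = 16: 2.131 × 0.894 / √16 = 0.48 at r = 0.6, and 2.131 × 0.632 / √16 = 0.34 at r = 0.8.

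The chance of nominal improvement is the upper tail beyond t of a noncentral t with n − 1 degrees of freedom and noncentrality (gain / SD of change) × √n. For example, a gain of 0.4 with r = 0.6 and n = 20 gives 0.4 / 0.894 × √20 = 2.0 and a probability of 47.6%.

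| Assumed gain (baseline SD) | n = 20, r = 0.6 to 0.8 | n = 16, r = 0.6 to 0.8 |
|---|---|---|
| 0 | 2.5% | 2.5% |
| 0.1 | 6.9% to 9.9% | 6.2% to 8.6% |
| 0.2 | 15.6% to 26.9% | 13.1% to 21.9% |
| 0.4 | 47.6% to 76.5% | 38.8% to 65.8% |

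These rows use the whole gain, g + s. The benefit of alternate letters is the move from one row to a lower one, not to the zero row. If half of a 0.4 SD gain were tied to the letters, for instance, 0.2 SD would remain and the third row would apply. The documents do not give that share.

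**Correlations.** For a shift c common to all participants, corr(X, change + c) = corr(X, change). A uniform practice gain therefore leaves the correlations planned in Section 9 unchanged.

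**The case against.** The case for leaving the plan alone is that this is a 20-person feasibility pilot using a standard letter set. Its primary outcomes are retention, adherence and the System Usability Scale. Cognitive change is exploratory and uncontrolled, so it would not be an effect estimate even with alternate forms. No paired test is planned, and every practice size above is assumed. Two form orders also add form-difference variance to individual change scores, which could weaken the planned correlations with adherence and proficiency.

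Most of this stands and limits the importance of the point. The variance cost is real but small: recording the order and adjusting for it handles the systematic part. The objection does not show that repeating the letters is better than alternating them.

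A reader might infer four stronger things that the documents do not support:

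- *All three cognitive tests repeat identical material.* Only the COWAT content is fixed. For the other two the protocol is silent, and silence is not a decision to reuse a form.
- *Practice pushes every score upward.* Trail Making is in seconds, where lower is better, and subtracting part A from part B may cancel some of the gain.
- *The mean changes are the effect size for the next trial.* Section 9 ties the powering work to the relationship of adherence and proficiency with clinical outcomes, which a common shift does not alter.
- *Practice is larger in less impaired participants and so distorts those correlations.* Nothing in the documents establishes this.

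**Conclusion.** The point holds for the COWAT. One letter set, two administrations about 12 weeks apart and no comparator mean that any letter-specific retest gain biases the mean change towards apparent improvement and cannot be told apart from the programme. For Trail Making and Digit Span the finding is only that the form at each visit is unspecified.

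The size cannot be derived from the documents. The illustrative range (about 7% to 77% nominal improvement at n=20, 6% to 66% at n=16, against 2.5%) depends on assumed gains and correlations and on a test the protocol does not contain. It describes the whole practice gain, of which alternate letters would remove only part. At the low end of the assumed range the gain is well inside the sampling error.

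This is a cheap improvement to an exploratory outcome. It does not touch the primary outcomes.

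**What to change.** 1. In the COWAT paragraph of Section 6, subsection 2, specify two matched letter sets. Alternate their order by enrolment number, and record the set used at each visit. Settle this before baseline testing, because the order cannot be counterbalanced afterwards.
2. In Section 9, report mean COWAT change as the average of the two order means, and adjust for order when correlating change with adherence and proficiency.
3. State which Trail Making layout and digit lists are used at each visit. If identical forms would otherwise be reused, treat them in the same way.
4. State that cognitive change may still include retest gain from familiarity with the task and setting, and is not an effect estimate for a later trial.

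The cost is obtaining matched forms, a field recording the set at each visit, some extra form-difference variance in individual change scores, and one degree of freedom for order. No visit or test is added.

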- If the system enables monitoring longitudinally of adherence, proficiency, and safety.
- If the system is acceptable and user-friendly for its intended use in the home setting.
- As an exploratory aim: if a 12-week training program using the Tele-TC platform leads to improvements in cognitive function, balance, physical activity, self-efficacy, health-related quality of life, and gait.

If this preliminary study leads to positive results, we will embark on a follow-up study to assess the potential clinical benefits of using the technology as part of a clinical intervention on cognition, balance, physical activity, gait, self-efficacy, and health-related quality of life.

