### Primary aims

- Aim 1: *To evaluate the feasibility, acceptability, and safety of a novel home-based Tele-TC intervention by tracking recruitment, retention, adherence, and adverse events.*
  - Hypothesis 1: We will be able to recruit 20 older adults with mild cognitive impairment and limit withdrawals to 20% or less.
  - Hypothesis 2: Participants will complete >60% of recommended Tele-TC sessions.
  - Hypothesis 3: Protocols for assessing safety can be developed and reliably administered, and preliminary evidence will support Tele-TC can be delivered safely.

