### **4. Subject Selection**

#### **Inclusion criteria:**

Eligibility criteria are purposefully broad to maximize generalizability of the study results. To be eligible to participate in the study, individuals will have to meet the following criteria:

- Men and women between 60 and 85 years old
- TC naïve (never practiced TC)
- With mild cognitive impairments (Montreal Cognitive Assessment (MoCA)-Blind score between 17 and 13).
- Self-reported ability to walk continuously for 15 minutes without an assistive device
- Working email address
- Prior experience with and current access to a computer, smart phone or tablet device

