**Figure 2: Flow Chart of the study.**

person. Study staff will explain all the study procedures, equipment, and the risks associated with them as outlined in the informed consent form (ICF). The devices will be provided to the subjects after consent.

Subjects will be provided among others with two mobile devices and requisite chargers, a tablet travel stand, tripod, two GeneActiv watches, 5 wearable sensors, each of them with elastic bands and with chargers and wires. Of the two mobile devices, one will be used to interact with the developed TC app and the other will be used an extra mobile device and stand for virtual visits and video recording.

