- Participants will be instrumented with 5 sensors (one on each limb and one on the trunk) and they will be following the instructions from the Tele-TC platform.

Study staff will use Zoom to communicate with subjects during the visits done remotely. The performance of TC exercises will also be videorecorded and scored using the proficiency metric described in our preliminary studies section to provide a gold standard. We will try to use the sensors during the remote visits, but if it is not possible, we will document the reasons and continue the TC exercises only with video.

Subjects will be asked to don one Smart GeneActiv watch by ActivInsights\* on their wrist to monitor activity during approximately a week after visits #1B and a week before visit #4.

We will ask the participants to send the GeneActiv back to the lab after wearing it. We will be sending another GeneActiv about two weeks before visit #4.

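### On the most natural reading of the calendar, the first activity-watch week is about training week 1, so the watch's change from baseline compares early with late training

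*Combined protocol and SAP*

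**What the plan says.** Section 6, item 2 (Assessments) has participants wear the GeneActiv watch "to monitor activity during approximately a week after visits #1B and a week before visit #4". The first watch is sent back after use, and another is posted roughly two weeks ahead of the last visit. Under the same item, participants at Visit #1B are taught the tablet program, receive the programmed devices and sensors, and are monitored doing TC with the platform.

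Section 5 gives the sequence: "After baseline testing, subjects will participate in the Tele-TC intervention", with follow-ups at about 4 and 8 weeks and "at a final assessment (visit #4) at 12 weeks". Section 6, item 3 describes a 12-week program of home practice on three or more days a week, 45 to 60 minutes each time, with frequency and duration logged by the platform.

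Section 6, item 7 lists activity level, separately from the PASE questionnaire, among the exploratory changes between baseline and post-intervention. The question behind it, in Section 1, is "if a 12-week training program using the Tele-TC platform leads to improvements in cognitive function, balance, physical activity", among other outcomes.

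**The concern.** A change from baseline needs a baseline taken before the intervention can act. The late watch week is placed before its visit and the early one after its visit. By the end of Visit #1B participants have the equipment and the instruction to begin, and no readable section provides a watch week before training.

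If practice is under way during the first watch week, the watch does not answer the Section 1 question about physical activity. It describes how activity moves between the start and the end of training. Two things are then lost from the reported change: the session time itself, and any change in other activity that begins as soon as training does. Section 9 expects these pilot data to support and help power a later trial, so a change labelled as from baseline could be carried forward as something it is not.

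**Working it through.** The plan gives no figure to reproduce. The check is a comparison of dates, followed by simple arithmetic on session time.

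**Inputs.** Watch windows: about one week after Visit #1B and one week before Visit #4 (Section 6, item 2). Practice: 3 sessions a week, the recommended minimum, of 45 to 60 min for 12 weeks (Section 6, item 3). Visit #4: 12 weeks (Section 5). The day of the first home session is not stated; call it d days after Visit #1B.

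**1. Calendar.** The visits run baseline, about 4 weeks, about 8 weeks, 12 weeks, which reads most naturally as counted from baseline. Twelve weeks of practice before a Visit #4 at week 12 leave 12 − 12 = 0 spare weeks. Practice then begins at about Visit #1B, the first watch week is about training week 1, and the second is about training week 12. If practice instead followed the watch week and Visit #4 stayed at week 12, 12 − 1 = 11 practice weeks would remain, or 3 × 11 = 33 sessions rather than 3 × 12 = 36. That does not match the 12-week program.

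**2. Session time in the watch change.** Prescribed practice is 3 × 45 = 135 to 3 × 60 = 180 min/week.
- Against a pre-training week, with full practice in the last week: +135 to +180 min/week.
- With equal practice in both watch weeks: 135 − 135 = 0 and 180 − 180 = 0 min/week.

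**3. Partial overlap.** With sessions spread evenly and full practice in the last week, the first watch week holds 3 × (7 − d)/7 sessions for d up to 7, so the share of the session-related change that is kept is d/7.
- d = 0: 0% kept.
- d = 3: 3/7 = 43% kept, which is 135 × 3/7 = 58 to 180 × 3/7 = 77 min/week.
- d = 7 or more: 100% kept.

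**4. Scale.** At an assumed 16 h of wear a day, a week is 7 × 16 × 60 = 6,720 min, and session time is 135/6,720 = 2.0% to 180/6,720 = 2.7% of it. At 24 h wear (10,080 min) it is 1.3% to 1.8%. The plan defines no watch metric, so the effect in watch units cannot be computed.

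**5. Watch beside PASE.** PASE asks about the preceding 7 days. If it is completed at the visits, it looks back from Visit #1B while the watch looks forward; at Visit #4 both cover about the same week. The two measures of physical activity would then estimate different contrasts.

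**The case against.** The strongest reply is that the overlap is not stated. No readable section gives the origin of the 12-week clock or the first session date, and "Figure 2: Flow Chart of the study" is a caption whose image is missing from the copy reviewed; it may settle the matter. Section 5 puts the intervention after baseline testing, and Section 6, item 7 treats activity level as collected at baseline, so the watch week may be meant as part of baseline with practice to follow. This stands, and a reader should not infer that the baseline is certainly contaminated. It does not remove the point, because that reading fits poorly with 12 weeks of practice before a visit at 12 weeks.

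Second, the minutes above are session time, which the platform already logs, and the sessions include seated warm-ups and rest. This also stands. What the log cannot recover is change in non-session activity that starts in week 1, and the documents give no basis for sizing it.

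Third, item 7 does not name the watch as the source of activity level. The watch remains the natural source, since PASE is listed separately and no other general activity monitor is described.

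A reader might also infer that the watch change could turn negative if practice fell off by the end. The documents do not support building on that. Their only adherence figure, "Participants will complete >60% of recommended Tele-TC sessions", is a benchmark for the whole program and says nothing of a decline from first week to last.

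**Conclusion.** The point holds as a conditional one of low weight. On the most natural reading of Sections 5 and 6, the first watch week is about training week 1, and what is reported as a change from baseline is a contrast of late with early training. With equal practice in both weeks, the session contribution is about 0 rather than +135 to +180 min/week, and other activity change that sets in during week 1 is absorbed into the baseline.

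This rests on three assumptions: the 12 weeks run from baseline, practice starts at about Visit #1B, and activity level means the watch measure. The minutes also assume prescribed practice and count all session time as activity.

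It would be too strong to infer that the trial lacks any pre-training measure of physical activity. PASE, if completed at Visit #1B, covers a pre-training week by self-report; the questionnaires go out by email link with no completion date fixed, hence the condition. The watch outcome is one of many exploratory outcomes in a single arm of 20 with descriptive analysis. The primary outcomes (retention, adherence and the System Usability Scale) are untouched.

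**What to change.** Reconcile Section 5 with Section 6, items 2, 3 and 7 by stating where the 12-week clock starts relative to the first watch week. If the two are already meant not to overlap, a clarifying statement is all that is needed, provided it also squares the 12 practice weeks with the date of Visit #4.

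If they do overlap, there are two ways forward.

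- **Collect the first watch week before Visit #1B**, mirroring the arrangement at Visit #4, so that watch and PASE cover about the same week at both ends. Posting a watch ahead of a visit is already planned for Visit #4. The costs are outward mailings to at least 20 people, some watch data from people who then fail in-person screening, and consent ahead of the visit. Section 5 now describes an "informed consent process in person, by phone or on Zoom Enterprise with a trained research assistant at the beginning of the baseline testing visit", and Section 6, item 1 describes consent in person, so both would need amending.
- **Keep the present timing and relabel.** Report the watch outcome as early training versus late training, not as change from baseline. Use the platform's log of practice frequency and duration to separate session time from other activity in both windows. State that this is a different contrast from PASE. The cost is a little extra processing of data already collected; a pre-training watch measure is still not obtained.

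The choice is best made before data collection, since a missed pre-training watch week cannot be recovered. When home practice begins remains for the sponsor to decide.
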